### 8.1.1 Criteria for the Calculation of Apparent Terminal Elimination Rate Constant and Half-life

The start of the terminal elimination phase for each participant will be defined by visual inspection and generally will be the first point at which there is no systematic deviation from the log-linear decline in concentrations.

The apparent terminal elimination rate constant ( $\lambda_z$ ) will only be calculated when a reliable estimate can be obtained using at least 3 data points, preferably not including  $C_{max}$ , and the adjusted coefficient for determination of exponential fit ( $R^2$ -adj) of the regression line is  $\geq 0.7$ . Parameters requiring  $\lambda_z$  for their calculation (eg,  $\text{AUC}_{inf}$ ,  $t_{1/2}$ , CL/F (Profile Day 1 only), and  $V_z/F$ ) will only be calculated if the  $R^2$ -adj value of the regression line is  $\geq 0.7$ .

The following regression-related diagnostic PK parameters will be determined where possible:

Parameter	Units	Definition
$\lambda_z$	1/h	apparent terminal elimination rate constant
$\lambda_z$ Upper	h	end of exponential fit
$\lambda_z$ Lower	h	start of exponential fit
$\lambda_z$ N	NA	number of data points included in the log-linear regression
$\lambda_z$ Span Ratio	NA	time period over which $\lambda_z$ was determined as a ratio of $t_{1/2}$
$R^2$ -adj	NA	adjusted coefficient for determination of exponential fit

NA = not applicable

Where possible, the span of time used in the determination of  $\lambda_z$  (ie, the difference between  $\lambda_z$  Upper and  $\lambda_z$  Lower) should be  $\geq 2$  half-lives. If the  $\lambda_z$  Span Ratio is  $< 2$ , the robustness of the  $t_{1/2}$  values will be discussed in the clinical study report (CSR).

### 8.1.2 Criteria for Calculation and Reporting of Area Under the Concentration-time Curve

The minimum requirement for the calculation of AUC will be the inclusion of at least 3 consecutive concentrations above the lower limit of quantification. If there are only 3 consecutive concentrations, at least 1 should follow  $C_{max}$ .

If the extrapolated area is  $> 20\%$ ,  $AUC_{inf}$  (and derived parameters) may be excluded from the summary statistics and statistical analysis at the discretion of the sponsor or pharmacokineticist.

For evaluation of food effect, if  $AUC_{inf}$  cannot be determined reliably for all participants, an alternative AUC measure, such as AUC to a fixed timepoint, may be used in the statistical analysis of food effect.

If the  $\tau$  PK blood sample is collected slightly early (ie, the 24-hour), the actual sampling time of the  $\tau$  sample may be used for the calculation of  $AUC_{\tau}$ . However, the  $AUC_{\tau}$  parameter will be calculated if the  $\tau$  sample is within 60 minutes of the nominal sampling time.

### 8.1.3 Calculation of Urinary Parameters

The amount of the dose administered recovered (Ae) in urine as CVL-354 for each urine collection interval ( $t_1-t_2$ ) will be calculated as the product of urine analyte concentration and urine volume. Where only urine sample weight is supplied, a specific gravity of 1 g/mL will be assumed, and it will be considered equivalent to urine volume.

A total cumulative  $Ae_{0-x}$  h will be calculated by summing the  $Ae_{t_1-t_2}$  values over the 0-x h interval, where x = the end of the dosing interval.

The percentage of the dose administered recovered over the time interval  $t_1$  to  $t_2$  ( $fe_{t_1-t_2}$ ) as CVL-354 will be calculated for each urine collection interval (equivalent to a dosing interval) as follows:

$$fe_{t_1-t_2} = (Ae_{t_1-t_2} / dose) \times 100\%$$

Cumulative  $fe_{0-x}$  h will be calculated by summing the  $fe_{t_1-t_2}$  values over the 0-x h period in the same manner as cumulative  $Ae_{0-x}$  h.

Renal clearance ( $CL_R$ ) will be calculated over 0-t2 according to the following formula, where cumulative Ae is calculable over the dosing interval (0-t2 equivalent to  $\tau$ ):

$$CL_R = Ae_{0-t_2} / AUC_{\tau}$$

#### **8.1.4 Criteria for Handling Concentrations Below the Limit of Quantification or Missing Concentrations for Pharmacokinetic Analysis**

Plasma concentrations below the limit of quantification (BLQ) will be assigned a value of 0 before the first measurable concentration and thereafter BLQ concentrations will be treated as missing. The following rules apply to the specific situations defined below:

- If an entire concentration-time profile is BLQ, it will be excluded from PK analysis.
- Where 2 or more consecutive concentrations are BLQ at the end of a profile, the profile will be deemed to have terminated and any further quantifiable concentrations will be set to missing for the calculation of the PK parameters, unless they are considered to be a true characteristic of the profile of the drug.
- If a predose plasma concentration is missing, it will be set to 0 by default within Phoenix WinNonlin for the first dosing day of all parts of the study (Study Profile Day 1).
- For multiple dose part of the study (Study Profile Day 14), if the analyte concentration at  $\tau$  (24 hours postdose) is missing, this may be substituted with the predose concentration. Similarly, if the predose concentration is missing then this may be substituted with the concentration at  $\tau$ .

Urine concentrations that are BLQ will be set to 0 for the calculation of  $Ae_{t1-t2}$ .

#### **8.1.5 Treatment of Outliers in Pharmacokinetic Analysis**

If a value is considered to be anomalous due to being inconsistent with the expected PK profile, it may be appropriate to exclude the value from the PK analysis. However, the exclusion of any data must have strong justification and will be documented in the CSR.

Any quantifiable predose concentration value on the first dosing day of all parts of the study (Study Profile Day 1) will be considered anomalous and set to missing for the PK analysis. This will be set to 0 by default in Phoenix WinNonlin.

For Cohort 3 of Part A, if the predose concentration is  $>5\%$  of  $C_{max}$  in the second treatment period, all PK concentration and parameter data will be excluded from the summary statistics and statistical analysis for that period.

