### 6.1.2 Food Effect Evaluation (Cohort 3)

Cohort 3 will be scheduled after completion of single dose escalation to evaluate the effect of food on CVL-354 exposures after a single 50 mg dose. The selected dose is 4-fold lower than the top single CVL-354 200 mg dose that is considered safe and tolerated. For evaluation of food effect, a 2-period crossover design will be utilized, with approximately 8 participants randomized to 1 of 2 sequences (fed/fasted or fasted/fed). The duration of each period will be 3 days, with a 2-day washout between Period 1 and Period 2.

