## Part A\* (SAD and Food Effect)

Parameter	Units a	Definition
AUC last	h*ng/mL	area under the concentration-time curve from time zero to the time of the last quantifiable concentration b
AUC 24	h*ng/mL	area under the concentration-time curve over the time interval 0 to 24 hours postdose b
AUC inf	h*ng/mL	area under the concentration-time curve from time zero extrapolated to infinity b, c
%AUC extrap	%	percentage of area under the concentration-time curve due to extrapolation from the last quantifiable concentration to infinity
C max	ng/mL	maximum plasma concentration
T max	h	time to maximum plasma concentration
t last	h	time of the last quantifiable concentration
t 1/2	h	apparent terminal elimination half-life
CL/F	L/h	apparent clearance of drug from plasma
V z/F	L	apparent volume of distribution during the terminal phase
DAUC last	h*ng/mL/mg	AUC last normalized by dose administered d
DAUC 24	h*ng/mL/mg	AUC τ normalized by dose administered d
DAUC inf	h*ng/mL/mg	AUC inf normalized by dose administered d
DC max	ng/mL/mg	C max normalized by dose administered d

a Units are based on concentration units (provided by the bioanalytical lab or preferred units for presentation of PK parameters) and dose units used in the study.

b The area under the concentration-time curve will be calculated using the linear trapezoidal rule for increasing concentrations and the logarithmic rule for decreasing concentrations (linear up/log down rule).

c Based on the last observed quantifiable concentration.

d Calculated by dividing the parameter by the dose (mg).

\* Concentration-time profile following each discrete single dose in Part A Profile Day 1, including all periods of the food effect evaluation.

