### **8.2 Presentation of Pharmacokinetic Data**

If the actual time of sample collection deviates from the nominal time by more than  $\pm 10\%$ , the plasma concentration will be flagged and excluded from the concentration summary statistics. Individual concentrations deemed to be anomalous will be flagged in the listings and excluded from the summary statistics.

For plasma concentration data, the following rules will apply:

- Values that are BLQ will be set to 0 for the calculation of summary statistics.

- Arithmetic mean or median values that are BLQ will be presented as 0.
- Concentrations will be reported to the level of precision in which they were received from the analytical laboratory.

For PK parameters, the following rule will apply:

- Geometric mean and coefficient of variation will not be calculated for  $t_{last}$  or  $T_{max}$ .

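### The PK plan's predose rule, read with its own definition of Profile Day 1, treats carry-over in later Part A periods as anomalous and conflicts with the Cohort 3 test at 5% of Cmax

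*SAP*

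**What the plan says.** Four statements in the PKAP bear on this.

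- **General rule (8.1.5).** "Any quantifiable predose concentration value on the first dosing day of all parts of the study (Study Profile Day 1) will be considered anomalous". These values are then "set to missing for the PK analysis. This will be set to 0 by default in Phoenix WinNonlin".
- **Meaning of the label (8.1, footnote to the Part A parameter table).** Profile Day 1 is described as "Concentration-time profile following each discrete single dose in Part A Profile Day 1, including all periods of the food effect evaluation".
- **Cohort 3 rule (8.1.5, directly after the general rule).** The trigger is a Period 2 predose value above 5% of Cmax. The consequence is stated as: "all PK concentration and parameter data will be excluded from the summary statistics and statistical analysis for that period".
- **Reporting (8.2).** "Individual concentrations deemed to be anomalous will be flagged in the listings and excluded from the summary statistics". BLQ plasma values enter the summaries as 0.

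PKAP 8.1.4 uses the same label for absent samples: "If a predose plasma concentration is missing, it will be set to 0 by default within Phoenix WinNonlin for the first dosing day". Cohorts 1 and 2 have up to four periods, at least 5 days apart (PKAP 6.1.1), and no carry-over criterion is given for them. For Cohort 3, "The duration of each period will be 3 days, with a 2-day washout between Period 1 and Period 2" (PKAP 6.1.2).

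**The concern.** In a crossover, a quantifiable predose concentration in Period 2 or later is the direct measurement of residual drug from an earlier dose. It is the reason for taking the sample. A rule that calls it anomalous in advance also sits badly with the opening of the same section, which asks for strong justification before data are excluded.

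Two things are at stake.

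1. **The food-effect comparison.** The mixed model (PKAP 9.2) has sequence, period and fed/fasted status as fixed effects and no carry-over term. The 5% exclusion is the only prespecified carry-over safeguard. Cohort 3 has about 8 participants and is open-label, so whether one Period 2 profile stays in should not be settled after the data are seen.
2. **What the tables show.** If quantifiable predose values are dropped and BLQ values count as 0, every summarised Part A predose value is 0 by construction. Washout would look complete whatever was measured.

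**Working it through.** The plan gives no figure to reproduce. The check has two parts: which profiles each rule reaches, and how large the effect could be.

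**1. Reach of the rules, using the footnote's definition of Profile Day 1**

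| Predose sample | General rule applies? | What a quantifiable value means | 5% test? |
|---|---|---|---|
| Part A, first period dosed | Yes | Unexpected: no earlier dose | No |
| Cohorts 1 and 2, Periods 2 to 4 | Yes | Carry-over | No |
| Cohort 3, Period 2 | Yes | Carry-over | Yes |
| Part B, Day 1 | Yes | Unexpected: Part A participants are excluded (Protocol 5.2, criterion 27) | No |

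The third row holds the conflict. One rule removes the value that the other must test, and no order or exception is stated. If the test is run on the zeroed value, it asks whether 0/Cmax exceeds 5%, which is never true.

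**2. Size**

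Inputs from the documents:
- Dose interval in Cohort 3: check-out is on Day 8 (Protocol Figure 2), which is Period 2 Day 3. The second dose is therefore on Day 6, and (6 − 1) × 24 = 120 h. Five days in Cohorts 1 and 2 is also 120 h.
- Sampling: predose, then 0.5, 1, 2, 3, 4, 6, 8, 12, 16, 24, 36 and 48 h.
- AUC: linear up, log down.

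Assumptions: one compartment, ka = 1/h, and a range of half-lives, because none is visible in the documents.

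Formulas: k = ln 2 / t½. Per unit dose, C(t) = ka/(ka − k) × (e^(−kt) − e^(−ka·t)). In Period 2, C2(t) = C(t) + C(t + 120). The tested ratio is C(120) / max C2.

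Worked example, t½ = 30 h: k = 0.0231 and ka/(ka − k) = 1.0237. C(120) = 1.0237 × 2^(−4) = 0.0640. The peak is at 4 h: 0.9146 + 0.0583 = 0.9729. The ratio is 0.0640/0.9729 = 6.6%.

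| t½ (h) | Predose / Cmax | Carry-over effect on Period 2 AUClast | Effect of zeroing on AUClast | 5% test on measured value | 5% test on zeroed value |
|---|---|---|---|---|---|
| 12 | 0.1% | +0.1% | −0.002% | no | no |
| 24 | 3.5% | +3.3% | −0.03% | no | no |
| 30 | 6.6% | +6.5% | −0.05% | yes | no |
| 36 | 9.9% | +10.3% | −0.07% | yes | no |
| 48 | 16.2% | +18.2% | −0.11% | yes | no |

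The measured ratio crosses 5% at a half-life of about 27 h. Simple decay gives nearly the same: 120/log2(20) = 120/4.32 = 27.8 h.

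**3. Cohort 2, highest dose**

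Each sequence has one placebo period (Protocol Table 8). I assume that the doses in Protocol Table 10 were given in ascending order. A participant on 200 mg in Period 4 then had one of three histories. At t½ = 30 h the ratios are:

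- placebo, 90, 150 mg: 5.2%
- 45 mg, placebo, 150 mg: 5.0%
- 45, 90 mg, placebo: 0.2%

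The mean is (5.2 + 5.0 + 0.2)/3 = 3.5%.

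**The case against.** **The scope may be narrower.** The phrase about the first dosing day could mean Period 1 only, which would remove the conflict. That reading is open, but the PKAP's own footnote points the other way. It would also leave no stated handling for quantifiable predose values in later periods, other than above 5% in Cohort 3.

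**The Cohort 3 rule may be an exception.** It is specific, follows the general rule directly, and makes sense only with a measured value. The general rule acts on the noncompartmental calculation, the Cohort 3 rule on the summaries and the model. This is the more natural reading and may well be what was intended. It is not stated, however, and it does nothing for Cohorts 1 and 2.

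**Nothing is erased.** A reader might infer that measured carry-over disappears. It does not: the value is missing for the PK analysis and absent from the summaries, but all concentrations are listed (PKAP 9.1) and anomalous ones are flagged. This stands.

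**Zeroing does not inflate exposure.** A reader might blame the rule for upward bias in later-period AUC. Any such bias comes from residual drug in the postdose samples and is there whether or not the predose value is zeroed. This also stands.

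**The food-effect ratio is partly protected.** Carry-over that is proportionally similar in both sequences would largely fall into the period effect. This limits the harm to carry-over that differs between sequences.

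**Excluding profiles in Cohorts 1 and 2 could do harm.** That analysis is descriptive, with about 6 active participants per dose, and exclusion would selectively remove slow eliminators. I agree, and the fix asks only for a flag.

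**Conclusion.** The point holds as a conflict of scope and order between stated rules. By the PKAP's own definition, the general rule covers later crossover periods, labels carry-over there as anomalous and takes it out of the summaries. It also collides with the Cohort 3 exclusion.

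The documents do not support saying that the exclusion is defeated. It fails only if zeroing comes before the test, and they do not say that it does.

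The direct numerical effect of zeroing is negligible: 0.11% of AUClast or less for half-lives up to 48 h. What may be lost is the trigger for the exclusion and the visibility of carry-over in the tables. The trigger matters only if the half-life exceeds about 27 h; below that, the test would not fire under either reading. That threshold rests on a one-compartment model, ka of 1/h and 120 h between equal doses. The sponsor holds the Part A PK results and can see at once which side of it the drug falls on. The wording conflict does not depend on the half-life.

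**What to change.** Amend PKAP 8.1.5 as follows.

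1. Limit the rule that sets a value to missing or 0 to each participant's first dose in the trial: the first Part A period dosed, or Part B Day 1.
2. State that the Cohort 3 test at 5% of Cmax uses the measured Period 2 predose concentration, before any value is set to missing.
3. Keep measured predose values in the profiles and the concentration summaries for Cohorts 1 and 2 in Periods 2 to 4, and for Cohort 3 Period 2 when at or below 5% of Cmax.
4. In Cohorts 1 and 2, flag predose values above 5% of Cmax without requiring exclusion.

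The absent-sample rule in PKAP 8.1.4 uses the same label, so its scope should be stated at the same time.

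The cost is wording only, with no new samples and no change to the model. The downside is that small non-zero predose values will appear in the later-period tables.

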### **8.2 Presentation of Pharmacokinetic Data**

If the actual time of sample collection deviates from the nominal time by more than  $\pm 10\%$ , the plasma concentration will be flagged and excluded from the concentration summary statistics. Individual concentrations deemed to be anomalous will be flagged in the listings and excluded from the summary statistics.

For plasma concentration data, the following rules will apply:

- Values that are BLQ will be set to 0 for the calculation of summary statistics.

- Arithmetic mean or median values that are BLQ will be presented as 0.
- Concentrations will be reported to the level of precision in which they were received from the analytical laboratory.

For PK parameters, the following rule will apply:

- Geometric mean and coefficient of variation will not be calculated for  $t_{last}$  or  $T_{max}$ .

### **8.2.1 Presentation of Urine Drug Concentration Data**

Urine drug concentrations will be listed only to the level of precision in which they were received from the analytical laboratory.

### **8.2.2 Presentation of Pharmacokinetic Parameters**

For the calculation of summary statistics of PK parameters, all not calculated (NC) values in a data series will be set to missing.

Individual PK parameters will be presented to three significant figures. For the calculation of summary statistics, data will be handled and presented as described in [section 9.1](#).

## **9 STATISTICAL METHODOLOGY**

### **9.1 General**

All PK concentrations and parameters will be listed.

Summary tables by treatment will be provided for all concentrations and PK parameters.

Summary statistics will only be presented for data where detailed in this PKAP. Summary statistics will include the arithmetic mean, standard deviation (SD), geometric mean, coefficient of variation (CV) of geometric mean, median, minimum (min), maximum (max), and number of observations (n) for concentrations and all PK parameters (except  $t_{last}$  or  $T_{max}$ , where geometric mean and CV of geometric mean will not be calculated). Summary statistics will be calculated for concentration and PK parameter data for participants included in the PK analysis set and will be stratified by treatment.

Summary tables, mean ( $\pm$ SD) figures, and overlaying individual figures will be provided for plasma PK concentrations. All figures will be produced on both linear and semi-logarithmic scales.

For the calculation of summary statistics for plasma concentrations, data will be used as received from the bioanalytical laboratory. For calculation of summary statistics for PK parameters, unrounded data will be used. Statistics will be reported to three significant figures with the exception of N and n which will be presented to the nearest integer. Individual PK parameters will be presented to three significant figures.

The full battery of summary statistics will only be calculated if there are at least three values in the data series. Zeros are considered to be values. If there are fewer than three values in the data

series, only min, max, and n will be presented. The other summary statistics will be denoted as NC. If the value of the arithmetic mean and/or median is BLQ, these will be presented as zero.

All statistical summaries and figures for concentration and PK parameter data will be performed using SAS software Version 9.4 or higher.

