3. OBJECTIVES AND ENDPOINTS

The primary and secondary objectives and corresponding endpoints are summarized in Table 6 (SAD portion) and Table 7 (MAD portion).

Additional exploratory endpoints may be evaluated during the trial, including food effect in the SAD portion, in the MAD portion, and the in the SAD and MAD portions. Banked biospecimens will be collected from consenting participants for potential exploratory research. Plasma and urine samples will also be obtained for metabolite scouting.

Table 6: Objectives and Endpoints - Part A (SAD)

Objectives	Endpoints		
Primary			
To evaluate the safety and tolerability of single ascending doses of CVL-354 administered orally to healthy participants	 Treatment-emergent AEs, including AEs potentially related to abuse Clinically significant changes in ECGs, vital signs, clinical laboratory assessments, and physical and neurological examination results Changes in suicidality assessed using the C-SSRS 		
Secondary	-1		
To evaluate the plasma pharmacokinetics of CVL-354 following single ascending doses administered orally to healthy participants	 Pharmacokinetic parameters of CVL-354 following single oral doses: C_{max} T_{max} AUC₂₄ AUC_{last} AUC_{inf} CL/F V_z/F t_½ 		
To evaluate the effect of food following single doses of CVL-354 administered orally to healthy participants	 Pharmacokinetic parameters of CVL-354 following single oral doses: C_{max} T_{max} AUC₂₄ AUC_{last} AUC_{inf} CL/F V_z/F t_{1/2} 		

Abbreviations: AE=adverse event; AUC=area under the concentration-time curve; CL/F=apparent clearance of drug from plasma; C_{max} =maximum plasma concentration; C-SSRS=Columbia-Suicide Severity Rating Scale; ECG=electrocardiogram; $t_{1/2}$ =apparent terminal half-life; SAD=single ascending dose; T_{max} =time to maximum plasma concentration; V_z /F=apparent volume of distribution during terminal phase.

Table 7: Objectives and Endpoints - Part B (MAD)

Objectives	Endpoints	
Primary		
To explore the safety and tolerability of multiple ascending doses of CVL-354 administered orally to healthy participants	 Treatment-emergent AEs, including AEs potentially related to abuse Clinically significant changes in ECGs, vital signs, clinical laboratory assessments, and physical and neurological examination results Changes in suicidality assessed using the C-SSRS 	
Secondary		

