4.1.1.2. Food Effect Evaluation (Cohort 3)

Cohort 3 will be scheduled after completion of single dose escalation to evaluate the effect of food on CVL-354 exposures after a single 50 mg dose. The selected dose is 4-fold lower than the top single CVL-354 200 mg dose that is considered to be safe and tolerated. For evaluation of food effect, a 2-period crossover design will be utilized, with approximately 8 participants randomized to 1 of 2 sequences (fed/fasted or fasted/fed). Details of fasted and fed conditions are provided in Section 5.3.1. Sentinel dosing will not be employed for evaluation of food effect.

Participants will remain domiciled after Check-in for both periods of the food effect evaluation. The duration of each period will be 3 days, with a 2-day washout between Period 1 and Period 2.

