9.4.3. Pharmacokinetic Analyses

All PK exposure parameters (eg, C_{max}, AUC) will be summarized by dose, where applicable, using descriptive statistics including the arithmetic mean, median, standard deviation, coefficient of variation, minimum and maximum values, Q1, Q3, and geometric mean.

For food effect assessment, the single dose of CVL-354 administered in fasted state is the reference treatment and the single dose of CVL-354 administered in fed state is the test treatment. Natural log-transformed dose-normalized AUC_{inf}, AUC_{last}, and C_{max} (for CVL-354) will be analyzed using a mixed effect model with sequence, period, and fast/fed status as fixed effects and participant within sequence as a random effect. Estimates of the adjusted mean differences (test-reference) and corresponding 90% CIs will be obtained from the model. Then they will be exponentiated to provide estimates of the ratio of adjusted geometric means (test/reference) and 90% CIs for the ratios.

Additional detail on the PK analysis will be provided in the SAP.

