### For Food effect:

The ln-transformed  $AUC_{inf}$ ,  $AUC_{last}$ ,  $AUC_{24}$  and  $C_{max}$  for CVL-354 will be analyzed using a linear mixed model. The model will include planned treatment sequence, period, and actual treatment (i.e., fast/fed status) as fixed effects, and participant within planned treatment sequence as a random effect.

For each PK parameter separately, the least squares mean (LSM) for each treatment, difference in LSMS between the fed and fasted treatments, and corresponding 90% CI will be calculated; these values will then be back-transformed to give the GLSM, ratio of GLSMs, and corresponding 90%.

Additionally, the pooled estimate (across treatments) of the within-subject CV will be calculated, and residual plots will be produced to assess the adequacy of the model(s) fitted.

Examples of the SAS code that will be used are as follows:

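### Tmax is a listed food-effect endpoint, but the plan specifies no within-participant fed-minus-fasted comparison, and so no interval or summary of individual shifts, for it

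*SAP*

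**What the plan says.** Protocol Section 3, Table 6, gives a secondary objective for Part A: "To evaluate the effect of food following single doses of CVL-354 administered orally to healthy participants". Its endpoints are Cmax, Tmax, AUC24, AUClast, AUCinf, CL/F, Vz/F and t1/2. SAP Table 1 and PKAP Section 5 repeat the list.

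The design gives pairs. In Protocol Section 4.1.1.2, "a 2-period crossover design will be utilized, with approximately 8 participants randomized to 1 of 2 sequences", so each completer has one fed and one fasted Tmax.

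The fed/fasted contrast is limited to exposure:

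- Protocol Section 9.4.3: "Natural log-transformed dose-normalized AUC_{inf}, AUC_{last}, and C_{max} (for CVL-354) will be analyzed using a mixed effect model".
- PKAP Section 9.2 adds AUC24. These parameters "for CVL-354 will be analyzed using a linear mixed model" with sequence, period and fed/fasted status as fixed effects. For each, the "difference in LSMS between the fed and fasted treatments, and corresponding 90% CI will be calculated".

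Tmax is not in that model. PKAP Section 9.1 supplies what it does get: "Summary tables by treatment will be provided for all concentrations and PK parameters". For Tmax that means mean, SD, median, minimum, maximum and n within each state; geometric mean and CV are left out. Individual values appear in Listing 16.2.6.1.4. PKAP Section 9.1 also confines summary statistics to data the PKAP details. The only food-effect analysis output in PKAP Section 13 is Table 14.2.1.5.

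**The concern.** Tmax is the listed parameter that shows directly whether a meal delays absorption; AUC and Cmax ratios do not show timing. A crossover is run so that each participant serves as his or her own control, yet for Tmax the planned tables describe the fed and fasted states separately.

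At stake is whether the report can say how large the meal-related delay is, how precisely it is known, and whether it is consistent across participants. This has some bearing on fixed-time assessments. Cohort 3 has a single post-dose standing blood pressure, at 2 hours. In Part B, doses on non-intensive days follow breakfast by at least 1 hour, and the post-dose vital signs on Days 4 and 7 are also taken at 2 hours. That link is indirect, because Cohort 3 uses a high-fat meal finished about 5 minutes before dosing and Part B a light breakfast.

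**Working it through.** The plan states no figure for Tmax variability or precision, so there is nothing to reproduce. Four checks follow.

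**1. Do the by-treatment tables determine the paired shift?** Assumed values, placed on the protocol's sampling times:

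- Fasted: 0.5, 1, 1, 1, 2, 2, 2, 3 h (sum 12.5, mean 1.56, median 1.5)
- Fed: 1, 2, 2, 3, 3, 4, 4, 6 h (sum 25, mean 3.13, median 3.0)

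Pair these in the order shown, then with the fed list reversed. The planned tables are identical.

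| | Same order | Reversed |
|---|---|---|
| Mean shift | 1.56 h | 1.56 h |
| Range of shifts | +0.5 to +3.0 h | -2.0 to +5.5 h |
| SD of shifts | 0.82 h | 2.32 h |
| t-based 90% CI | 1.01 to 2.11 h | 0.01 to 3.12 h |

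The mean shift can be recovered by subtraction. Its precision and the spread of individual shifts cannot.

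**2. What if a Period 2 profile is excluded?** PKAP Section 8.1.5 removes a Cohort 3 participant's Period 2 data when the predose value exceeds 5% of Cmax. Suppose, in the same-order pairing, the last participant is fasted in Period 1 and loses the fed value of 6 h.

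- Subtracting the tables: 19/7 - 12.5/8 = 2.71 - 1.56 = 1.15 h
- Paired mean over the 7 complete participants: (12.5 - 3)/7 = 1.36 h

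The tables now cover different people, so subtraction no longer gives the paired shift.

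**3. How much precision does pairing buy?** With n pairs, within-participant SD σw and between-participant SD σb:

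- Paired SE = √(2σw²/n)
- SE if the two summaries are treated as independent = √(2(σb² + σw²)/n)
- Ratio = √(1 + (σb/σw)²)

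| σb, σw (assumed) | Paired SE, n = 8 | Unpaired SE | Ratio |
|---|---|---|---|
| 0.5, 1.0 h | 0.50 h | 0.56 h | 1.12 |
| 0.5, 0.5 h | 0.25 h | 0.35 h | 1.41 |
| 1.0, 0.5 h | 0.25 h | 0.56 h | 2.24 |

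The plan itself computes no unpaired SE for Tmax. The comparison is with what a reader could build from its tables.

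**4. Is a design-matched interval feasible?** Take each participant's Period 1 minus Period 2 Tmax. With food effect δ and period effect π, its location is π + δ in the fed/fasted sequence and π - δ in fasted/fed. The difference between sequences is 2δ, free of π. With 4 per sequence there are 4 × 4 = 16 between-sequence differences; half their median is the Hodges-Lehmann estimate of δ. Among the 70 equally likely allocations:

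- P(U ≤ 1) = 2/70, so half the 2nd and 15th ordered differences give coverage 1 - 4/70 = 94.3%.
- P(U ≤ 2) = 4/70, so half the 3rd and 14th give 1 - 8/70 = 88.6%.

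If one participant is lost (4 versus 3, 35 allocations), the two levels are the same: 1 - 2/35 = 94.3% and 1 - 4/35 = 88.6%. These figures assume no ties. Sampling at 0.5, 1, 2, 3, 4, 6, 8 and 12 h and later (PKAP Section 6.5) makes ties likely, so coverage is approximate.

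A signed-rank interval on the 8 raw differences would attain 92.2% or 89.1%, but it omits the period term used for every other modelled food-effect parameter.

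**The case against.** The strongest case against runs as follows.

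- **The shift is available.** A reader might infer from the missing contrast that the Tmax shift is never estimated, or that the pairing is thrown away. The documents do not support that. With complete pairs, subtracting the means gives the mean within-participant shift, and with about 8 participants every individual shift can be read from the listing. What stands is narrower: no interval and no summary of shifts is planned, and subtraction depends on complete pairs.
- **The trial is descriptive.** Protocol Section 9.1 plans no hypothesis tests, and the Section 3 text even mentions food effect among exploratory endpoints. But the plan already gives 90% intervals without tests for AUC and Cmax, so an interval for Tmax fits the same approach.
- **Being listed does not promise a contrast.** CL/F, Vz/F and t1/2 are in the same list and also get only by-treatment summaries. This is correct, and the omission breaks no stated commitment. The case for Tmax is that nothing in the modelled set measures timing.
- **Extra analyses are allowed.** PKAP Section 4 permits supplementary analyses, and the table shells are in a separate document not available here. Permission is not prespecification.
- **No decision depends on it.** No passage ties a decision to Tmax under food, and Cohort 3 may run in parallel with Part B. This stands and keeps the point minor.

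**Conclusion.** The point holds as a small gap in the analysis plan. Tmax is a named food-effect endpoint measured in pairs, and the PKAP specifies no paired estimate, interval or summary of individual shifts for it.

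Its size cannot be fixed from the documents, which give no Tmax variance. Under assumed between/within SD ratios of 0.5 to 2, pairing improves the standard error by about 1.1 to 2.2 times. A reader might take the upper end as the expected gain; only the assumed ratios produce it, and at a ratio of 0.5 the gain is about 12%. The hour values in the pairing example are likewise assumed and show only that the planned tables do not determine the paired result.

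The nonparametric interval assumes an additive period effect, no carryover and the same distributional shape in both sequences. Nothing here affects the planned AUC and Cmax comparisons.

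**What to change.** Add one sentence to PKAP Section 9.2 and one row to Table 14.2.1.5. For Cohort 3 participants with both periods evaluable, report:

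- the median and range of the fed-minus-fasted Tmax differences;
- the period-adjusted Hodges-Lehmann estimate, from period differences compared between sequences and halved;
- a nonparametric interval of about 90%, with no p-value.

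State in advance which attainable level will be used, for example the lowest that is not below 90%, and report the attained coverage as approximate when there are ties. State the number of pairs used.

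The cost is that sentence, that row and a wide interval at n of about 8. No new data are needed. While editing, correct the SAP Section 9.4 abbreviation list, which defines Tmax as the time to the last quantifiable concentration, in conflict with SAP Table 1 and PKAP Section 8.1.
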